#### 7.3.4 Day -1 to Day 2 ('Admission' Days)

#### 7.3.4.1 Admission Day -1

Participants will be admitted to the SURC clinic at the NYSPI where they will complete the PHQ, BDI-II, Substance Use assessment, urine drug screen, concomitant medication review and AE monitoring. Each participant will then undergo the NCT to confirm opiate naivety based on COWS score.

#### 7.3.4.2 Admission Day 0

Participants will be scheduled for administration of the OLANI as outlined in section 7.1.1.3. After a review of concomitant medications and vital signs are obtained, participants will be fitted with the iv cannula to aid in the collection of blood sample for the first 48 hours. There shall be no use of heparin to keep the cannula clear as this may affect the blood analysis of naltrexone and 6- $\beta$ -naltrexol. Processing and storage of blood samples shall be done as per section 7.2.4.1.

The recorded dose time (0 hour) will be the time at which the procedure will be completed. Naltrexone blood samples (see section 7.2.4.1) will be collected at the following time points: 3 hours  $\pm 60$  min, 6 hours  $\pm 60$  min, and 12 hours  $\pm 60$  min. The actual time of each PK sample collection shall be recorded.

Participants will also be monitored for AEs.

## 7.3.4.3 Admission Day 1

Naltrexone blood samples (see section 7.2.4.1) will be collected at 24 hours  $\pm 2$  hours after the OLANI procedure. The actual time of each PK sample collection shall be recorded.

Participants will also be monitored for AEs, have a review of concomitant medications and have a Wound Site/ Implant Site Assessment as per 7.1.1.4.

At this time, participants will have the option of remaining an inpatient or being discharged from the SURC clinic and returning for the 48-hour observation (Admission Day 2).

## 7.3.4.4 Admission Day 2

Naltrexone blood samples (see section 7.2.4.1) will be collected at 48hours  $\pm 2$  hours after the OLANI procedure. The actual time of each PK sample collection shall be recorded.

Participants will also be monitored for AEs, have a review of concomitant medications and have a Wound Site/ Implant Site Assessment as per 7.1.1.4.

Remaining inpatient participants will be discharged from the SURC clinic.

All participants will be provided with a timetable for their follow-up visits, which will be carried out at the Clinilabs clinic.

## 7.3.5 Follow-Up Day 4 to 540

Participants will be instructed to attend the Clinilabs clinic to continue study procedures on an outpatient basis as per the protocol time points outlined in Table 7-1. There are allowable variations in actual day of collection as long as the variation is recorded. The following will be collected at all time points: Concomitant medical review, PK blood collection, AE monitoring, vital signs (Blood pressure, heart rate, respiratory rate, and oral body temperature) and a Wound Site/Implant Site assessment (see section 7.1.1.4).

The following will also be collected on day 28 and then monthly as outlined in Table 7-1, PHQ & BDI-II, C-SSRS, FBC, FCP, UA, Pregnancy test (initial with urine with serum testing used to confirm positive results), substance use reporting (self-report using the Quantitative Substance use Inventory) and UDS.

Note: As appropriate, participants may be seen for follow-up visits at the SURC clinic (i.e. if clinically indicated or if traveling to the Clinilabs clinic presents a hardship to a participant).

**SARS-CoV-2 Note:** This study is being conducted in New York, NY; a location heavily impacted by the COVID-19 pandemic. Therefore, for the safety of study participants, the IRB requested on 21 April 2020 that in-persons study visits be stopped and replaced with telephone or video visits. Thus, where in-person study visits are not possible, safety will be monitored remotely. This change means that for some participants, certain procedures (e.g. PK blood draws), may be missed during the time of the public health emergency. Table 7-1 has been updated to indicate which procedures will be captured by telephone/video visits and which procedures may be missed due to COVID-19. In case there are safety concerns that need in-person evaluation to determine best course of action, such as new-onset implant site-reaction or site drainage, then an in-person visit at the clinic will be conducted.

This change was implemented on 27 April 2020 and all missed visits/procedures are being tracked. In person visit will resume immediately when deemed safe and appropriate by the IRB.

## 7.3.6 Final Study Visit

All participants will be required to attend the SURC clinic for a final visit with a study PI as outlined in Table 7-1. The final visit will be scheduled as soon as possible after two non-detectable PK samples have been obtained, or after Day 540 visit has occurred.

#### 7.3.7 Early Termination Visit

Any participants that are withdrawn will be required to attend the SURC clinic for an early termination /withdrawal visit as outlined in Table 7-1. Participants will be advised of their options as outlined in in section 5.4.2.

A follow-up visit may be conducted 30 days after the last scheduled on-study visit and is required only if a participant has ongoing AEs or laboratory abnormalities at the last on-study visit. An in-clinic follow-up visit must be conducted 30 days after the last scheduled on-study visit for an AE requiring laboratory testing for participants with the following conditions at the last on-study visit: ongoing AEs, SAEs regardless of attributability, any laboratory abnormalities considered to be AEs or potentially harmful to the participant. For in-clinic follow-up visits, assessments performed should reflect what is considered medically necessary to assess the event(s).

#### 7.3.8 Unscheduled Visit

It is anticipated that some participants may miss or be delayed to some of their appointments. Every effort will be made to obtain blood samples at the scheduled dates, but blood samples will be accepted if they are taken late, with allowances made in the statistical analysis for this. Participants who miss appointments will be contacted by phone to encourage them to return for as many appointments as possible. However, some dropouts are also anticipated so additional participants will be recruited to get the correct totals for analysis.

Participants will be asked to complete the following; vital signs, concomitant medication review, wound site/implant site assessment and AE monitoring (see Table 7-1). Additional assessments performed at Unscheduled visits are at the discretion of a study physician.

#### 7.3.9 PK Follow-up Visit

PK follow-up visit may be conducted 30 days after the last monthly PK visit 540 days, if the participant has detectable naltrexone plasma levels. Follow-up visits will continue until two consecutive monthly naltrexone blood levels recorded at <0.1 ng/mL are received from the lab and recorded. If the latest PK levels are pending, participants will continue to make follow-up visits (see Table 7-1).

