# **4 STUDY DESIGN AND ENDPOINTS**

#### 4.1 DESCRIPTION OF THE STUDY DESIGN

This pilot study is a phase I/II, open label, single-arm pharmacokinetic trial of the OLANI in healthy participants without a DSM 5 - Substance Related Disorders classification. PK data will be collected in all participants until 2 consecutive monthly naltrexone blood levels recorded at <0.1 ng/mL, it is anticipated that this will occur by Day 540. Participants will be required to undergo a Naloxone Challenge Test (NCT) to confirm absence of physiological dependence on opioids before administration of the study medication. Participants will be recruited, treated and followed up at the SURC clinic at the NYSPI.

All participants will be treated with a double administration of a 1.8g ( OLANI.

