#### 4.2 STUDY ENDPOINTS

#### 4.2.1 Primary Endpoint

• The collection of at least 75% pharmacokinetic blood time points including 2 consecutive monthly naltrexone blood levels recorded at <0.1 ng/mL, in 10 participants.

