8. **PK follow-up visit** may be conducted 30 days after the last monthly PK visit 540 days, if the participant has detectable naltrexone plasma levels. Follow-up visits will continue until two consecutive undetectable naltrexone plasma levels (defined as naltrexone blood levels of <0.1 ng/mL) are recorded.

- 9. AE follow-up visit may be conducted 30 days after the final study visit and is required only if a participant has ongoing AEs or laboratory abnormalities. A follow-up visit must be conducted for an AE requiring laboratory testing for participants with the following conditions: ongoing AEs, SAEs regardless of attributability, any laboratory abnormalities considered to be AEs or potentially harmful to the participant.
- 10. Institution = SURC clinic for all visits up to and including the initial 48 hours, and Final Visit or Early Termination Visit (as applicable). Additional follow up visits may also occur at the SURC clinic when appropriate. Further, a Discharge CRF is to be completed at the time of participant discharge (i.e. approximately 24 or 48 hours after the procedure).
- 11. For analysis purposes, **Baseline** is defined as Screening Visit 2. However, the following measures from Screening Visit 1 should also be included in the Baseline analysis: PHQ, BDI-II, CSSRS Lifetime, and Vital Signs.

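### The rules for PK sampling after Day 540 conflict with the promise in 4.1 and the two-level primary endpoint, so a participant first below 0.1 ng/mL at Day 540 has no assured route to the second level

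*Combined protocol and SAP*

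**What the plan says.** Section 4.1 sets the design rule: "PK data will be collected in all participants until 2 consecutive monthly naltrexone blood levels recorded at <0.1 ng/mL". It adds that this is expected to happen by Day 540. The primary endpoint in 4.2.1 uses the same criterion, "including 2 consecutive monthly naltrexone blood levels recorded at <0.1 ng/mL, in 10 participants", together with at least 75% of the PK time points. Section 10.4.2 limits the primary analysis to participants who meet both conditions.

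The last two scheduled monthly PK samples are Day 510 and Day 540 (Table 7-1, note 7). For later sampling, 7.3.9 opens with: "PK follow-up visit may be conducted 30 days after the last monthly PK visit 540 days, if the participant has detectable naltrexone plasma levels". It continues: "Follow-up visits will continue until two consecutive monthly naltrexone blood levels recorded at <0.1 ng/mL are received from the lab and recorded". Its last sentence covers outstanding results: "If the latest PK levels are pending, participants will continue to make follow-up visits". Note 8 to Table 7-1 repeats the entry rule and the continuation rule ("Follow-up visits will continue until two consecutive undetectable naltrexone plasma levels") and defines undetectable as below 0.1 ng/mL.

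Section 7.3.6 says when a participant leaves: "The final visit will be scheduled as soon as possible after two non-detectable PK samples have been obtained, or after Day 540 visit has occurred".

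**The concern.** The endpoint asks for two levels, but the entry rule for extra sampling asks a different question: whether naltrexone is still detectable. The two part company for someone who has just crossed the threshold. That participant is no longer detectable under note 8, yet holds only one of the two levels.

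The verb in the entry rule is also permissive. The protocol knows the difference, because 7.3.7 sets *may* against *must* for follow-up visits. And 7.3.6 makes the passing of Day 540 sufficient for the Final Visit, with no exception for participants short of two levels.

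At stake is whether a participant who attends throughout can be classed as a non-completer only because the decline was slow or because one late draw was missed. The summary of changes for version 0.6 gives defining the time to undetectable naltrexone as the reason for extending the study. The boundary at Day 540 is therefore where the rule most needs to be clear.

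**Working it through.** **Inputs.** Schedule: 6 hourly and 25 daily time points (3.1). Last monthly samples: Day 510 and Day 540 (Table 7-1, note 7). Threshold: below 0.1 ng/mL (4.2.1, note 8). Enrolment 20, expected completers 10, that is 50% (5.3.1).

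**Plan's own figures.** 10 / 0.50 = 20, which matches the stated enrolment. The time points total 6 + 25 = 31, and 75% of 31 is 23.25, so at least 24 samples are needed. Meeting that count does not meet the two-level condition.

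**Applying the rules to four late courses** (no earlier pair of qualifying levels):

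- *Below 0.1 at Day 510 and at Day 540.* Two levels are held. The endpoint condition is met and all sections agree.
- *At or above 0.1 at Day 510, below 0.1 at Day 540.* One level is held. The participant is undetectable under note 8, so the entry condition in 7.3.9 fails. 7.3.6 permits the Final Visit. 4.1 says sampling continues.
- *Day 510 draw missed, below 0.1 at Day 540.* The position is the same. Section 7.3.5 and note 14 accept missed PK draws when visits are remote because of COVID-19, so this case is not confined to slow decline.
- *At or above 0.1 at Day 540.* No qualifying pair is held. The entry condition is met but the visit is optional. 7.3.6 permits the Final Visit. 4.1 says sampling continues.

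In the last three cases the operational rules and 4.1 give different answers.

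**Can the Final Visit supply the second level?** Table 7-1 marks PK collection at the Final Visit. However, 7.3.6 times that visit as early as possible after its trigger, while monthly PK visits are 30 days apart with a ±10-day window. Nothing says that a Final Visit sample counts as a monthly level.

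**Size.** Each lost completer is 1/10 = 10% of the target. The documents do not give the time at which levels fall below 0.1 ng/mL, so the number affected cannot be calculated. As an illustration only, let q be the share of would-be completers who get no second sample, and treat participants as independent. Expected completers are 20 × 0.50 × (1 − q). The chance of reaching 10 is the binomial upper tail P(X ≥ 10), with n = 20 and p = 0.50 × (1 − q):

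- q = 0: 10.0 expected, probability 0.588
- q = 5%: 9.5 expected, probability 0.498
- q = 10%: 9.0 expected, probability 0.409
- q = 20%: 8.0 expected, probability 0.245

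The values of q are assumptions. The figures show only that a target equal to the expected count has no reserve.

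**The case against.** The best defence is that the passages, read together, give one stopping rule. Section 7.3.9 and note 8 both say that visits go on until two consecutive levels are recorded, 4.1 applies that to everyone, and 7.2.3 ties the end of blood collection to the same event. On this reading *may* means only that not everyone will need the visit, and 7.3.6 sets no deadline, so the Final Visit can come after PK follow-up. A site following 4.1 would take the sample. This stands far enough that one cannot say such a participant will be denied the second level. It does not remove the conflict: the continuation sentence says how long follow-up lasts, while the sentence before it says who enters.

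The pending-results sentence also helps. Samples can be shipped when more than 50 are available (7.2.4.1). If all 20 participants gave one sample a month, that would take more than 50 / 20 = 2.5 months, so a Day 540 result could well be outstanding at Day 570 and the participant would stay in follow-up. Shipment could be faster when others are in the dense early sampling. This protection is real but incidental, since it depends on laboratory turnaround and not on the participant's endpoint status.

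A reader might go further and infer that AUC and T>MEC would come to describe only faster releasers. The documents do not support that. Section 10.4.3 states no completer restriction for these parameters, and 10.3 refers to all enrolled participants and a 75% rule without the two-level condition. T>MEC turns on 1.33 ng/mL, so it does not need a second sample below 0.1 ng/mL.

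**Conclusion.** The point holds as an inconsistency that should be resolved. The entry rule in 7.3.9 and note 8, and the exit rule in 7.3.6, do not carry out what 4.1 states and what 4.2.1 and 10.4.2 require. Taken literally, they leave a participant first below 0.1 ng/mL at Day 540 outside PK follow-up, and make follow-up optional for one still at or above it.

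The consequence is limited to the completer count and to confirming the time to below 0.1 ng/mL (time to C0). How many participants are affected is unknown, and may be few or none given the expectation in 4.1. Any count would rest on an assumed distribution of time to below 0.1 ng/mL. The conclusion itself rests only on the wording and on note 8's definition of undetectable. It merits correction because it touches the primary endpoint, the target leaves no reserve, and the remedy is small.

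**What to change.** - In 7.3.9 and note 8, replace the detectability condition and the permissive verb. PK follow-up visits will take place every 30 days after Day 540 for any participant who has not yet recorded two consecutive monthly levels below 0.1 ng/mL and who agrees to continue.
- In 7.3.6, have the Final Visit follow the second such level. It should follow Day 540 without that level only if the participant declines further sampling.
- In 4.2.1 or 10.4.2, state that samples from post-540 follow-up visits count toward the primary endpoint, and say whether a Final Visit sample can serve as the second monthly level.

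The Protocol Summary's participant duration of 540 days should carry a matching note.

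The cost is wording in a few places and possibly a few extra visits. The visit type is already in Table 7-1 and its payment is already set in 7.9. The date of the last participant's last visit may move back by one or more months.

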#### 7.3.10 AE Follow-up Visit

A follow-up visit will be conducted 30 days after the last scheduled on-study visit. This visit is required only if a participant has ongoing AEs or laboratory abnormalities at the last onstudy visit (see Table 7-1). An in-clinic follow-up visit must be conducted 30 days after the last scheduled on-study visit for an AE requiring laboratory testing for participants with the following conditions at the last on-study visit: ongoing AEs, SAEs regardless of attributability, any laboratory abnormalities considered to be AEs or potentially harmful to the participant. For in-clinic follow-up visits, assessments performed should reflect what is considered medically necessary to assess the event(s). All other participants that will have additional questions or concerns about the fate of the implant will also be encouraged to come for a follow-up meeting with a study physician.

#### A PILOT PHARMACOKINETIC TRIAL OF THE O'NEIL LONG ACTING NALTREXONE IMPLANT CONFIDENTIAL Go-Medical Protocol GM0017: (Ver. 0.13; 11 June 2020)

	Screening Visit 1 	Screening Visit 2 	Recruitment Visit 	Admission Day -1 	Admission Day 0 	Admission Day 1 & 2 	Day 4  (±1 day)	Day 8  (±2 days)	Day 14, 21, 35, 42 & 49  (±3 days)	Day 28 & 56  (±3 days)	Monthly PK Visit  (±10 days)	Final Visit 	Early Termination / Withdrawal 	Un- scheduled Visit 	PK Follow- up 	AE Follow- up 
AE Monitoring		X	X	Х	X	х	X	X	Х	X	Х	X	Х	Х	X	X
Urine Drug Screen		X		Х						Х	Х	Х			Х	
Recent Drug Use- Baseline (RDU)		X														
Quantitative Substance Use Inventory	2 2			X						X	X	X		Х	X	
Naloxone Challenge Test			24  0	Х	2		2 2								S	- (s 2-
COWS Baseline, 10 Minutes, 20 Minutes, 30 Minutes				х				~ ~ ~ ~ ~ ~ ~ ~ ~ ~ ~ ~ ~ ~ ~ ~ ~ ~ ~								
Subcutaneous Implant (Dosing) EX	2°				Х								6. 10		2. 3	
Vital Signs (Height, Weight, BMI)	Х	1											83	28 N		
Vital Signs with weight 					Х		Х	X	Х	Х	X	Х	Х	Х	Х	Х
Wound Site/ Implant Site Assessment						X6	X	X	X	x	x	X	x	х	x	

1. Inclusion/exclusion criteria will only be reviewed at Screening Visit 2 and the Recruitment Visit.

2. C-SSRS will be used to assess suicidal risk. Lifetime risk will be assessed at screening visit 1, with subsequent visits assessing risk since last visit (SLV).

3. A blood sample will be taken for NTX & 6BN at Screening Visit 2.

4. Pregnancy testing will be conducted on all females of child bearing potential on serum at screening, subsequent testing will be carried out on urine samples with serum testing used to confirm positive urine results as per section 7.2.1.

5. Initial 48 hours PK Sampling - Blood samples will be collected at the following time points: Baseline screening visit, 3 hour ±60 min, 6 hour ±60 min, 12 hour ±60 min, 24 hour ±2 hours and 48 hour ±2 hours after the implant procedure. The actual time of each PK sample collection should be recorded.

6. Wound site/implant site assessment for day 1 (24h) and day 2 (48) will take place within ±2hours.

7. Monthly PK visit - Blood samples will be collected at the following time points: Day 90, 120, 150, 180, 210, 240, 270, 300, 330, 360, 390, 420, 450, 480, 510 & 540.

8. **PK follow-up visit** may be conducted 30 days after the last monthly PK visit 540 days, if the participant has detectable naltrexone plasma levels. Follow-up visits will continue until two consecutive undetectable naltrexone plasma levels (defined as naltrexone blood levels of <0.1 ng/mL) are recorded.

- 9. AE follow-up visit may be conducted 30 days after the final study visit and is required only if a participant has ongoing AEs or laboratory abnormalities. A follow-up visit must be conducted for an AE requiring laboratory testing for participants with the following conditions: ongoing AEs, SAEs regardless of attributability, any laboratory abnormalities considered to be AEs or potentially harmful to the participant.
- 10. Institution = SURC clinic for all visits up to and including the initial 48 hours, and Final Visit or Early Termination Visit (as applicable). Additional follow up visits may also occur at the SURC clinic when appropriate. Further, a Discharge CRF is to be completed at the time of participant discharge (i.e. approximately 24 or 48 hours after the procedure).
- 11. For analysis purposes, **Baseline** is defined as Screening Visit 2. However, the following measures from Screening Visit 1 should also be included in the Baseline analysis: PHQ, BDI-II, CSSRS Lifetime, and Vital Signs.

#### A PILOT PHARMACOKINETIC TRIAL OF THE O'NEIL LONG ACTING NALTREXONE IMPLANT CONFIDENTIAL Go-Medical Protocol GM0017: (Ver. 0.13; 11 June 2020)

- 12. Satellite Location 1 = Columbia University Medical Center (CUMC), [name]
- 13. Satellite Location 2 = Clinilabs, [name] for all visits after the initial 48-hour time-point
- 14. Changes Due to COVID-19: During the public health emergency, some of the monthly follow-up visits may occur by telephone/video only. The following safety assessments will occur during these remote study visits: concomitant medication review, PHQ (BDI-II), C-SSRS1 (since last visit), AE monitoring, Qualitative Substance Use Inventory and wound site/implant site assessment (self-reported) done via video link, if possible. Conversely, the following assessments/procedures may be missed because of having remote study visits: safety labs, PK blood collection, pregnancy test, urine drug screen, vital signs/weight.
- 15. Unscheduled Visits: Vital signs, concomitant medication review, wound site/implant site assessment and AE monitoring are to occur at all Unscheduled Visits. Additional assessments performed are at the discretion of a study physician.
- 16. Vital Signs: Blood pressure, heart rate, respiratory rate, and oral body temperature will be measured after the subject has been in a seated position for at least 5 minutes. Note: After a subject's last visit, the Disposition CRF must be completed.

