#### 5.4.2.1 Participant Monitoring and Removal from Study

Medical staff will assess and communicate with the study PI the appropriateness for continuation in the research study on a continuous basis and will remove from the trial participants with significant clinical deterioration or noncompliance of a type which could be dangerous. Criteria for removal from the study will include:

1. Clinical deterioration which cannot be managed safely in the context of outpatient treatment. This would include a participant who becomes suicidal, or a participant

who goes on severe drug binges (including non-opiate drugs), endangering him/herself.

- 2. Elevation of liver enzymes > 3 times normal. The PI or a study physician is available 24 hours/day by phone and/or beeper in case of emergency.
- 3. Participant becomes pregnant. In case of incidental pregnancy, the participant will remain in the study and will be followed until the resolution of pregnancy. To reduce unnecessary procedures, we will stop PK blood draws, unless clinically indicated, however the safety monitoring will continue. In addition, we will collect safety information related to the pregnancy and birth outcomes. After finding an incidental pregnancy the removal of the implant will be offered to the participant and the participant will decide how best to proceed in consultation with her obstetrician. The decision regarding the pregnancy will affect the decision whether or not to remove the implant at any point during the pregnancy. The risk of anesthesia differs during different times during pregnancy, however the risks of anesthesia and the risks of removal are both minimal.

If a participant becomes pregnant, PK labs will no longer be collected, but the participant will be followed for safety monitoring for the remainder of the study.

For those who withdraw from the study, (data collection and / or treatment) there are two main options:

- **Option 1:** Withdrawing from data collection and no further contact with study personnel. This carries the least amount of risk, with option 2 carrying some risk.

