#### 7.2 LABORATORY PROCEDURES/EVALUATIONS

#### 7.2.1 Clinical Laboratory Evaluations

Samples will be collected and sent for analysis to Lab Corp.

For the following test, 4.5 mL of blood will be collected in 1 tube (lavender top EDTA tube):

• [FBC] Full Blood Count: RBC, WBC, Hematocrit, Hemoglobin, Platelet Count, Eosinophils, Basophils, Monocytes, Neutrophils, Lymphocytes, Mean Corpuscular Volume (MCV), Mean Corpuscular Hemoglobin Concentration (MCHC), Mean Corpuscular Hemoglobin (MCH), Reticulocytes, Red cell distribution width (RDW), immature granulocytes

For the following tests, 5 mL of blood will be collected in 1 tube (red/grey mottled top gel barrier SST tube):

• [FCP] Full Chemistry Panel with Liver Function Tests: Glucose, Uric Acid, Blood Urea Nitrogen (BUN), Creatinine, Sodium, Potassium, Chloride, Calcium, Phosphorus, Protein Total, Albumin, Globulin, Albumin/Globulin A/G Ratio, Bilirubin (total), Bilirubin (direct), Bilirubin (indirect), Alkaline Phosphatase, Lactate Dehydrogenase (LDH), AST (SGOT), ALT (SGPT), GGT, Iron, Total Cholesterol, Triglycerides, HDL Cholesterol, LDL Cholesterol (calculated), Magnesium, CO2, CPK, Amylase, Lipase For the following tests, 5 mL of blood will be collected in 1 tube (lavender top EDTA tube):

- Hepatitis A IGG
- Hepatitis B Serology
- Hepatitis C Serology

For the following test, 5 mL of blood will be collected in 1 tube (red/grey mottled top gel barrier SST tube):

• *HIV Serology* 

For the following tests, a sample of urine is collected:

- UA (Urinalysis) including urine color, appearance, bilirubin, urobilinogen, WBC esterase and a microscopic examination (WBC, RBC, epithelial cells, mucus threads, bacteria)
- LEU (Leucocytes), NIT (Nitrite), PRO (Protein), pH, BLD (Blood), SG (Specific Gravity), KET (Ketones), GLU (Glucose)
- [UDS] Full drug screen including morphine, oxycodone, methadone, cocaine, amphetamines, hydromorphone, hydrocodone, codeine, methamphetamines, thc, benzodiazepines, fentanyl and buprenorphine assay.

**Pregnancy test**: For all female participants, a blood test is done initially, with urine tests done monthly afterwards. A blood test will be used to confirm a positive urine result.

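### Table 7-1 note 14 lets the monthly pregnancy test lapse at remote COVID-19 visits without a substitute, which can delay detection of an unrecognised pregnancy by about 30 days per missed test

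*Combined protocol and SAP*

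**What the plan says.** Section 7.2.1 sets the routine for female participants: "a blood test is done initially, with urine tests done monthly afterwards". Note 4 to Table 7-1 adds that "subsequent testing will be carried out on urine samples with serum testing used to confirm positive urine results". The table schedules post-implant tests at Day 28 and Day 56, at the monthly PK visits and at the Final Visit. It also marks a test under Unscheduled Visit and PK Follow-up. Note 7 gives the monthly visits as "Day 90, 120, 150, 180, 210, 240, 270, 300, 330, 360, 390, 420, 450, 480, 510 & 540", with a window of ±10 days.

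Note 14 covers visits held by telephone or video during the public health emergency. It first lists what will still be done remotely, including "wound site/implant site assessment (self-reported) done via video link, if possible". It then lists what "may be missed because of having remote study visits: safety labs, PK blood collection, pregnancy test, urine drug screen". Among the columns that carry a pregnancy test, note 14 is attached to the Monthly PK Visit and the Unscheduled Visit, and not to Day 28/56, Final Visit or PK Follow-up.

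The SARS-CoV-2 note in section 7.3.5 explains that the IRB asked on 21 April 2020 for in-person visits to stop, and that the change took effect on 27 April 2020. It says that "all missed visits/procedures are being tracked" and that "In person visit will resume immediately when deemed safe and appropriate by the IRB". In-person visits stay available for safety concerns that need them.

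On the consequence of a positive test, section 5.4.2.1 states: "After finding an incidental pregnancy the removal of the implant will be offered to the participant". The same section provides for consultation with an obstetrician, collection of pregnancy safety data and an end to PK draws. Section 8.4.3 requires reporting to the treating physician, the investigator, the IRB and the DSMB.

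**The concern.** The participants are healthy volunteers with no expected benefit (section 2.3.2), carrying an implant that cannot simply be stopped. Monthly testing is the plan's way of finding a pregnancy the woman has not noticed. Note 14 allows that test to lapse for as long as visits are remote, with nothing in its place.

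The safeguards that remain do not detect an unrecognised pregnancy. Dual contraception (section 5.2) lowers the chance of conception. Adverse-event questioning at remote visits relies on the woman knowing. The in-person exception needs someone to have raised a concern. The acceptance of late samples in section 7.3.8 is about blood samples.

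Every protective step depends on detection, so a later test means a later removal offer, obstetric consultation and report. Sections 5.4.2.1 and 8.4.3 both note that anesthesia risk varies over the course of a pregnancy, so timing is not irrelevant on the protocol's own account.

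**Working it through.** **Inputs.** Monthly visits are on Days 90 to 540, 30 days apart, ±10 days (Table 7-1 and note 7). Day 28 and Day 56 have a window of ±3 days (Table 7-1). The enrolment target is 10 women (section 5.3.1). The remote measure began on 27 April 2020 (section 7.3.5), and this protocol version is dated 11 June 2020.

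**Plan's own schedule.** Monthly visits: (540 − 90)/30 + 1 = 16, each 30 days after the last. Day 28 to Day 56 is 28 days, and Day 56 to Day 90 is 34 days. The stated monthly frequency is reproduced.

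**Share of tests under note 14.** For a woman followed to Day 540 the scheduled post-implant tests are Day 28 + Day 56 + 16 monthly + Final = 19. Note 14 covers 16, and 16/19 = 84%. This counts the tests that may be missed, not those that will be.

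**Gap between tests after k consecutive misses.**

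- Between monthly visits: 30(k + 1) days, ±20 because each end may move by 10.
- Starting from Day 56: 34 + 30k days, ±13 (3 at one end, 10 at the other).

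| Misses k | Monthly gap, days (range) | Gap from Day 56, days (range) |
|---|---|---|
| 0 | 30 (10–50) | 34 (21–47) |
| 1 | 60 (40–80) | 64 (51–77) |
| 2 | 90 (70–110) | 94 (81–107) |

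**Added delay against the planned schedule.**

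- Pregnancy detectable at the first missed visit: 30k days, so 30 for one miss and 60 for two. With windows, one miss adds 10 to 50 days.
- Two misses, detectable only at the second missed visit: 30 days.
- Detectable only after the last miss: 0 days.

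If the time at which a pregnancy becomes detectable is assumed uniform over the gap, the mean added delay is (30 + 0)/2 = 15 days for one miss and (60 + 30 + 0)/3 = 30 days for two.

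**Calendar.** 27 April to 11 June 2020 is 3 + 31 + 11 = 45 days, which contains one or two visits at 30-day spacing. That these visits were remote is an assumption. No end date is given for the remote period.

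**The case against.** The strongest reply is that this is a disclosed emergency measure taken at the IRB's request. It applies to some monthly visits only, misses are tracked, and in-person visits return once the IRB agrees. The next in-person monthly visit has its own test, as does the Final Visit, which is outside note 14. An unscheduled visit can include a test at the physician's discretion. The 84% figure describes eligibility, and participants leave monthly follow-up after two consecutive naltrexone levels below 0.1 ng/mL. The 30-day figure is the unfavourable case; under the uniform assumption it averages about 15 days per miss. Harm requires conception despite dual contraception, in at most 10 women, and unrecognised by the woman. By Day 90 the period of about 10 days in which removal is straightforward is long past (section 5.4.2.1, Option 2), and the protocol describes the risks of anesthesia and removal as minimal. A site can be viewed on video, whereas a pregnancy test needs a specimen, so the two are not strictly comparable.

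Most of this stands and limits the size of the point. It does not remove it. The IRB request, as reported, concerned in-person visits; the protocol does not say that pregnancy testing was meant to lapse. The next in-person test is the end of the gap, not a limit on its length. Tracking records a miss without repairing it. The specimen argument is weak for this test, since it is already done on urine and needs serum only to confirm a positive, unlike safety labs or PK blood.

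**Conclusion.** The concern holds, as a low-cost improvement to participant safety. Note 14 allows 16 of 19 scheduled post-implant tests to be missed, with no substitute, catch-up test or cap on consecutive misses. The nominal test interval becomes 60 days after one miss and 90 after two, and detection can be delayed by 30 days per consecutive miss.

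These delays are conditional on contraceptive failure, on the woman not recognising the pregnancy, and on the pregnancy being detectable at the missed visit. They are not expected delays. The documents give no pregnancy rate, no count of women of child-bearing potential in monthly follow-up during the remote period, and no gestational deadline for removal, so an expected number of cases cannot be derived. The consequence is a later start to the removal offer, consultation and reporting, not a lost removal window. No endpoint or PK analysis is affected. The consent pages are not in the review copy, so any instruction there to report a suspected pregnancy could not be checked.

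**What to change.** In note 14, remove the pregnancy test from the procedures that may be missed and add it to the assessments done remotely, for example: *pregnancy test (females of child-bearing potential): mailed home urine kit, result reported at the telephone or video visit and entered on the CRF; any positive result leads to an in-person visit for serum confirmation.* Serum confirmation is already required by section 7.2.1 and note 4. This restores the planned 30-day interval (10 to 50 days with windows).

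Cost: one line in note 14, one CRF field, and 10 × 1 = 10 to 10 × 2 = 20 kits if all 10 women have one or two remote visits. The ceiling is 10 × 16 = 160 kits if every monthly visit were remote. The downside is reliance on a self-read, self-reported result until the next in-person visit; note 14 already accepts self-report for the implant site. That kits can be mailed is an assumption, since the documents do not address it.
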